### 6.6.3 Completed Cases Population

The Completed Cases (CC) population will include all ITT subjects who complete 30-day follow-up. The CC population will also include ITT subjects who experience failure of the primary effectiveness endpoint prior to the beginning of the 30-day follow-up timepoint, irrespective of their length of follow-up.

## 7 STATISTICS AND DATA ANALYSIS

### 7.1 Statistical Methodology

The objective of the statistical design for this study is to evaluate the safety and effectiveness of the Lava LES, as assessed in comparison to literature-derived performance goals. The safety and effectiveness performance goals were determined from a literature review of publications on treatment of bleeding peripheral vessels. A total of 67 publications comprising 2102 patients were included in this review.

### 7.2 Primary Safety Endpoint

The primary safety endpoint is the 30-day rate of MAE, defined by the occurrence of any one of the following events between enrollment and 30 days after the index procedure:

1. Ischemia or infarction of the target territory;
2. Non-target embolization;
3. Allergic reactions to Lava;
4. Catheter breakage;
5. Catheter entrapment.

See **Section 5.1**, above, for a complete description of the elements of the primary safety endpoint.

### 7.3 Primary Effectiveness Endpoint

The primary effectiveness endpoint is Clinical Success, defined as absence of bleeding from a target lesion after embolization with the Lava LES, without the need for emergency surgery, re-embolization, or other target lesion reinterventions within 30 days of the index procedure. Absence of bleeding is defined as no BARC Type 3 or greater bleeding occurring after the index procedure, either

persistent or recurrent. The ascertainment of persistent or recurrent BARC Type 3 or greater bleeding does not include bleeding that occurred prior to the conclusion of the index procedure.

See **Section 5.2**, above, for a complete description of the primary effectiveness endpoint.

#### 7.4 Study Success Criteria

The study will be deemed successful if both the primary effectiveness and primary safety hypotheses are met. For the primary effectiveness endpoint, the lower limit of the one-sided 97.5% confidence interval must be greater than 72%. For the primary safety endpoint, the lower limit of one-sided 97.5% confidence interval must be great than 82%.

#### 7.5 Secondary Endpoints

The following secondary endpoints will be assessed in the study:

1. Assessment of each element of the primary safety endpoint (MAEs) as individual components;
2. Symptomatic ischemia in the target territory that does not require intervention;
3. All-cause mortality;
4. Bleeding-related mortality (attributable to bleeding in a target territory);
5. Open surgical conversion for persistent or recurrent bleeding;
6. Device-related serious adverse events;
7. Procedure-related serious adverse events;
8. Access site hematoma (>5cm in longest axis);
9. Access site false aneurysm;
10. Units of red blood cells transfused after administration of Lava;
11. Duration of the index procedure, total and after administration of Lava;
12. Contrast administered during index procedure;
13. Fluoroscopy time during index procedure;
14. Length of stay in the intensive care unit after the index procedure;
15. Length of hospitalization, total and after the index procedure.

#### 7.6 Subject Level and Lesion Level Analyses

The ITT dataset will be used for all safety endpoints. Each safety-related endpoint will be assessed on a subject-level basis; expressed as the number of subjects experiencing at least one event divided by the number of subjects with evaluable observations.

The CC dataset will be used for all effectiveness endpoints. Categorical effectiveness endpoints will be expressed as the number of Target Lesions meeting the effectiveness criteria divided by the number Target Lesions with evaluable observations. Continuous effectiveness endpoints will be assessed with mean or median and standard deviation or range, as appropriate for the distribution of data. Certain

effectiveness endpoints will be assessed on a lesion-level basis; for example, the primary effectiveness endpoint of Clinical Success. Other effectiveness endpoints will be assessed at the subject level; for example, measures related to resource utilization including procedure duration, contrast volume administered, and fluoroscopy time.

## 7.7 Missing or Incomplete Data

Every effort will be made to minimize the amount of missing data. Recognizing the difficulty of avoiding some missing data, however, data imputation methods with sensitivity imputation analyses will be carried out. Safety endpoint analyses will include all subjects experiencing at least one component of the safety endpoint or with follow-up to the lower limit of the follow-up window for the 30-day time point (i.e., the denominator will be adjusted for missing data). Target Lesions with unavailable effectiveness data will be assumed to have missing data at random and will be imputed by random selection with replacement of data from Target Lesions with complete data. The robustness of the multiple imputation outcome will be tested with a tipping point analysis encompassing all possible imputation outcomes.

## 7.8 Derivation of the Safety and Effectiveness Performance Goals

A literature search identified 67 publications reporting outcome for 2102 patients treated with embolotherapy for peripheral arterial hemorrhage.h A variety of embolic agents were used in the publications. Results were tabulated for technical success, clinical success, 30-day mortality, rebleeding, and non-target territory ischemia. Weighted averages were calculated as the number of patients with a specific type of event, divided by the number of patients with evaluable observations for that event type.

### 7.8.1 Safety Performance Goal

The safety performance goal is based on the available data from the literature review, as well as the Society of Interventional Radiology (SIR) Quality Improvement Guidelines for Percutaneous Embolization document. The SIR document estimated a 2.5% to 8.0% (average 4.0%) rate of symptomatic ischemia after embolotherapy, and a non-target territory embolization rate of approximately 2.5%. Assuming a 1% rate for each of the three other MAE elements (allergic reaction to embolic agent, catheter breakage, inability to withdraw the catheter), a composite rate of 10% was estimated for the 30-day MAE primary safety endpoint. Based on this, a safety success rate analysis was estimated in the range of 88%-92%. Using the sample size of 101 patients derived for the study hypothesis for primary effectiveness, one-sided 97.5% lower Wilson-score confidence limits were calculated based on safety success rates in the clinical study varying in the range of 88.1%-92.1% and are shown in Table 4 below. Assuming that the safety success rate is

h The literature review was performed by BlackSwan Vascular and was included in the preparatory materials for the Q-submission meeting on June 7, 2019 (Q181438/S002). See Attachment 1 for list of references.

90.1% and the sample size is 101, the lower 97.5% confidence limit is 82.7%. Based on this analysis, a prespecified performance goal for the above-mentioned safety endpoint was chosen to be 82%.

**Table 4. Lower Confidence Limit for Varying Safety Success Rates**

Sample Size	# of Successes	Safety Success Rate	Lower 97.5% Wilson-score Confidence Limit
101	93	92.1%	85.1 %
101	92	91.1%	83.9 %
101	91	90.1%	82.7 %
101	90	89.1%	81.5%
101	89	88.1%	80.4%

### 7.8.2 Effectiveness Performance Goal

The objective of Lava LES embolotherapy is to occlude feeding vessels to bleeding target lesions. Clinical Success, the primary effectiveness endpoint, averaged approximated 80% in the 51 publications that reported the endpoint (**Attachment 1**). This rate was consistent with the expected outcomes reported in the Society of Interventional Radiology document. An 8% margin was used to assign a effectiveness performance goal of 72%.

### 7.9 Sample Size

The study is powered for the primary effectiveness endpoint of Clinical Success. Based upon a one-sided 97.5% exact binomial test using a significance level of 0.025, the literature-derived performance goal of 72%, and an anticipated observed success rate of 84%, the required sample size to achieve a level of 80% power is 101 Target Lesions. Assuming a 10% attrition rate through 30 days, a total of 113 subjects will need to be enrolled. (**Table 5**).

 The anticipated Clinical Success rate of 84% was estimated after discussions with the Sponsor's scientific advisors.

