Sample Size Calculation	
The study is powered for the primary effectiveness endpoint of Clinical Success. Using the literature-derived performance goal of 72%, anticipating an observed success rate of 84%, and based upon a one-sided 97.5% exact binomial test with a significance level of 0.025, the required sample size to achieve a level of 80% power is 101 Target Lesions. Assuming a 10% attrition rate through 30 days, a total of 113 subjects will need to be enrolled.
 
Similarly, for primary safety endpoint, based on a literature-derived performance goal of 82% and an anticipated observed success rate of 92%, using a sample size of 101 provides 80% power to detect a difference of 9.9% using a one-sided exact binomial test with a significance level of 0.025.

Analytical Sets	
The regulatory submission will be based on an approximate sample size of 113 subjects. The safety endpoints will be assessed in the Intent-to-Treat dataset. The effectiveness endpoints will be assessed in the Completed Cases dataset.

Pre-Enrollment Testing	
 
• Medical history
 

	
 
Physical examination with vital signs and directed peripheral vascular examination
 
Laboratory assessment
 
Diagnostic angiogram at time of the planned index procedure, performed prior to the point of enrollment in the study. Eligibility is, in part, based upon the angiographic findings.
 

Follow-Up Schedule	
Subjects have required follow-up evaluations at the following time points:
 
 
1. Hospital discharge;
 
2. <math>30 \pm 7</math> days after the index procedure. This evaluation can be performed via telephone with a member of the investigational site's research staff or with an in-person visit with the Investigator.
 

Clinical Events Committee	An independent Clinical Events Committee (CEC) will review all primary safety endpoint events, unanticipated adverse device effects, and other important safety occurrences as specified in the CEC Charter.
Data Safety Monitoring Board	An independent Data Safety Monitoring Board (DSMB) will review safety data from the study at predetermined time points and as deemed necessary by the Sponsor or the DSMB Chair. The DSMB will make recommendations on protocol modifications and continuation of the study.
Study Principal Investigators	[name] MD [name] MD

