### **Handling of Missing Data**

All attempts will be made to limit the amount of missing data. For all analyses of the primary endpoints, the number of observations available will be reported so the reader can assess the impact of missing data. In general, and for the primary endpoint analyses, missing data will not be imputed and analyses will be based on available data. For missing values on the primary safety endpoint, an adjustment to the denominator will be made based on the amount of evaluable data. For each visit (or reporting time point), the occurrence rate will be calculated as the number of subjects with certain endpoint occurrence term over the number of evaluable subjects. The evaluable subjects at each reporting time point include all subjects who are enrolled by the snapshot date and

- 1) had an endpoint occurrence within (on or before) the reporting cutoff days (30 days), or
- 2) had a follow-up at or after the lower limit of the reporting window (23 days), or
- 3) the withdrawal consent date/recorded lost-to-follow-up date at or after the lower limit of the reporting window.

Sensitivity analyses will be performed to assess the impact of missing data and potential correlation in the data for the primary endpoints. Three different sensitivity analysis are planned: (1) As described in the protocol, Target Lesions with unavailable effectiveness data will be assumed to have missing data at random and will be imputed by random selection with replacement of data from Target Lesions with complete data. (2) A tipping point analysis will be conducted in which lesions or subjects censored without an event prior to 30 days follow-up are sequentially imputed as failures at the time of censoring. (3) A generalized estimating equation (GEE) logistic regression model will be used to estimate clinical success taking into account potential correlation of multiple Target Lesions within a subject using an exchangeable working correlation structure. The analyses for all the secondary endpoints will not include imputation for missing data, and no formal statistical hypotheses will be tested.

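### The sample size assumes losses unrelated to outcome, but the protocol's effectiveness set and both documents' safety denominator drop mainly event-free losses, so power at 10% attrition may fall short of the stated 80%

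*Protocol*

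**What the plan says.** **Sample size.** Protocol 7.9 uses "Based upon a one-sided 97.5% exact binomial test using a significance level of 0.025", with "the literature-derived performance goal of 72%, and an anticipated observed success rate of 84" percent, and concludes that "the required sample size to achieve a level of 80% power is 101 Target Lesions". It continues: "Assuming a 10% attrition rate through 30 days, a total of 113 subjects will need to be enrolled". SAP 3.2 repeats the calculation. For safety (goal 82%, anticipated 92%), the protocol Synopsis says that "using a sample size of 101 provides 80% power to detect a difference of 9.9" percentage points.

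**Effectiveness denominator, protocol.** Section 6.6.3 takes ITT subjects who finish 30-day follow-up and then adds: "The CC population will also include ITT subjects who experience failure of the primary effectiveness endpoint prior to the beginning of the 30-day" timepoint, however short their follow-up.

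**Effectiveness denominator, SAP.** Section 3.3 defines the set as ITT subjects who finish 30-day follow-up and stops there. It has no clause for early failures.

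**Safety denominator, both documents.** Protocol 7.7: "Safety endpoint analyses will include all subjects experiencing at least one component of the safety endpoint or with follow-up to the lower limit" of the 30-day window. SAP 3.4.1 counts a subject who "had an endpoint occurrence within (on or before) the reporting cutoff days (30 days"), or who was followed to day 23 or later, or whose withdrawal or loss was recorded on or after day 23.

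**Missing data.** SAP 3.4.1 bases the primary analyses on available data. Its sensitivity analyses are resampling from complete lesions, a tipping-point analysis and a GEE model.

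**The concern.** Dividing 101 by 0.9 allows for a smaller evaluable set but leaves the success rate in that set unchanged. Under protocol 6.6.3 and the safety rule, that rate does change. A unit that fails and is then lost stays in as a failure. A unit that is event-free when lost before the window leaves both numerator and denominator. Even if loss has nothing to do with outcome, the evaluable set is enriched for failures and the observed proportion falls below the true 30-day rate.

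At stake is a pivotal study that is likelier to miss a performance goal than its stated power suggests, for a device that meets the planning assumptions. Both goals must be met, so a shortfall on either endpoint matters.

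**Working it through.** **Inputs from the documents.** One-sided exact binomial test at 0.025. Effectiveness 72% vs 84%, safety 82% vs 92%. N = 101 evaluable, 113 enrolled, 10% attrition (protocol Synopsis, 7.9 and Table 5; SAP 3.2).

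**Assumptions the documents do not supply.** 84% and 92% are true 30-day rates. There is one lesion per subject. Loss is independent of outcome. The day-23 limit applies to both endpoints. The timing of failures and losses is varied.

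**Step 1: the plan's own figures.**
- Effectiveness, n = 101: success needs at least 82; exact alpha 0.0227; power 81.9%. No smaller n reaches 80%. 101/0.9 = 112.2, rounded up to 113. All six rows of protocol Table 6 reproduce.
- Safety, n = 101: success needs at least 91; alpha 0.0181; power 81.6%, or 80.6% at a true 91.9% (the 9.9-point difference).

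The stated figures are correct for their inputs.

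**Step 2: the rate in the evaluable set.** Let p be the true success rate, d the share lost before day 23, and f the share of lost units' failures that were recorded before loss. Then

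- successes kept = p(1 − d)
- failures kept = (1 − p)(1 − d(1 − f))
- expected observed rate = successes kept / (successes kept + failures kept)

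With d = 0.10 and f = 1:
- Effectiveness: 0.84 × 0.9 = 0.756; 0.756/(0.756 + 0.16) = 82.5%; expected n = 113 × 0.916 = 103.5.
- Safety: 0.92 × 0.9 = 0.828; 0.828/(0.828 + 0.08) = 91.2%; expected n = 113 × 0.908 = 102.6.

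**Step 3: power.** Exact power at each evaluable n, using that n's own critical value, averaged over the binomial distribution of n.

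| Scenario (113 enrolled) | Effectiveness (protocol 6.6.3) | Safety |
|---|---|---|
| 10% lost before day 23, all their failures recorded | 67.5% | 73.0% |
| same, two-thirds recorded | 71.7% | 76.0% |
| same, half recorded | 73.8% | 77.5% |
| same, one-third recorded | 75.8% | 79.0% |
| 10% spread over days 0–30, failures at day 0 | 72.0% | 76.8% |
| same spread, failures in week 1 | 73.5% | 77.8% |
| same spread, failures uniform over 30 days | 78.3% | 80.9% |
| Loss neutral to outcome | 79.5% | 81.7% |

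In the spread rows (by simulation) only 10% × 23/30 = 7.7% are lost before day 23. The rest count as evaluable.

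**Step 4: SAP 3.3 read literally.** If subjects who fail and then do not complete are also removed, deletion is neutral and effectiveness power is about 79–81%. That is achieved only by discarding recorded failures.

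**Step 5: direction of error.** At a true effectiveness rate of 72%, the chance of passing is 0.0055 (all failures recorded) to 0.0102 (half recorded), against 0.0186 with neutral loss. All are below 0.025.

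**Step 6: do the planned sensitivity analyses address it?** Resampling from complete lesions draws from the same failure-enriched set. Tipping-point imputation turns censored units into failures, which can only lower the estimate. GEE deals with lesions within a subject. None uses the event-free follow-up time of those lost. SAP 3.4.3 allows time-to-event methods, but only for secondary endpoints.

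**The case against.** - **The sample size is not miscalculated.** This stands. The 101, the 113 and Table 6 all reproduce.
- **The plan calls 84% and 92% anticipated observed rates.** If they already describe the evaluable set, the stated power holds. This stands as a condition. However, neither document says the rates were adjusted for selective deletion, and protocol Table 5 labels 84% simply as the anticipated rate.
- **A reader might infer that both primary denominators keep every recorded failure in both documents.** They do not. SAP 3.3 lacks the failure clause, and the day-30 criterion in SAP 3.4.1 is introduced for the safety endpoint. For effectiveness, the shortfall arises only under protocol 6.6.3.
- **A reader might take 67% and 73% as the study's actual power.** They require every failure among lost units to precede the loss, and every loss to precede day 23. Protocol 7.9 speaks only of attrition through 30 days, and no event timing is given. Nor is the range a strict bound: if a tenth of all 113 were removed and all were event-free, power would be 63.3% and 71.6%.
- **Up to four lesions per subject are allowed (protocol 8.3).** At 1.1 lesions per subject (124 lesions) effectiveness power is about 72–79%, and at 1.2 (136 lesions) about 76–82%, with all to half of lost units' failures recorded. These figures ignore within-subject correlation, which would take back some of the gain.
- **The bias is conservative.** This stands. It is a risk to the sponsor, and the documents do not support reading it as a threat to type I error.

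**Conclusion.** The point holds in limited form. The selective deletion is explicit in protocol 6.6.3 for effectiveness and in both documents for safety, and the attrition adjustment does not allow for it. Under the assumptions listed, power is roughly 67–78% for effectiveness and 73–81% for safety. Much of that spread reflects timing that the documents do not give. The 80% claim stands if successes and failures are lost equally, or if 84% and 92% are rates in the evaluable set.

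The two effectiveness denominators conflict, and the choice between them moves power materially. The SAP wording restores it, but at the price of leaving out known failures. Severity is moderate: a positive result would remain valid, but the stated power is conditional and the condition is not written down.

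**What to change.** 1. Reconcile SAP 3.3 with protocol 6.6.3 so that recorded early failures are counted in the effectiveness set.
2. In the protocol Synopsis, protocol 7.9 and SAP 3.2, say that 80% power holds only if successes and failures are lost equally, or if 84% and 92% are rates in the evaluable set. Give the lower range alongside, with its timing and one-lesion-per-subject assumptions.
3. In SAP 3.4.1, add a prespecified sensitivity analysis for both primary endpoints: the 30-day Kaplan-Meier rate with a one-sided 97.5% log-log lower limit, a variance robust to lesions within subject, and event-free losses censored at last contact. State the independent-censoring assumption, and say how event-free deaths are handled, since in this population they may violate it.

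The cost is wording in both documents, one extra analysis and a less favourable stated power. No extra patients are needed. Item 3 does not change the primary test or its power; it shows how far the deletion rule moved the estimate.

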**Table 5. Sample Size – Primary Effectiveness Endpoint**

Clinical Success	
Performance Goal	72%
Anticipated Clinical Success rate	84%
Significance level	.025
Statistical test	One-sided exact binomial test
Desired power level	80%
Required sample size (Target Lesions)	101
Target Lesions required, assuming 10% attrition through 30 days	113

Calculations for the required sample size for the anticipated success rate for Clinical Success, ranging from 80% to 85% appear in **Table 6**, below.

**Table 6. Sample Size Estimates for Varying Rates of Anticipated Success with the Lava LES**

One-sided Alpha	Power	Clinical Success ( $H_0$ )	Anticipated Success ( $H_A$ )	Sample Size Estimate	Sample Size with 10% Attrition
0.025	80%	72%	80%	227	253
0.025	80%	72%	81%	179	199
0.025	80%	72%	82%	142	158
0.025	80%	72%	83%	118	132
0.025	80%	72%	84%	101	113
0.025	80%	72%	85%	79	88

## 7.10 Study Hypotheses

Success or failure of the study will be based on the primary effectiveness and safety endpoints, with descriptive assessment of the primary and secondary safety endpoints. The primary effectiveness endpoint of Clinical Success will be assessed for all Target Lesions in the Completed Cases dataset and will be calculated on a per lesion basis.

$H_0: P_E \leq PG_E$ , versus

$H_A: P_E > PG_E$

Where  $P_E$  is the proportion of Target Lesions with Clinical Success and  $PG_E$  is the effectiveness performance goal (**Section 7.8.2**).

The primary safety endpoint of freedom from major adverse events will be assessed for all subjects in the ITT population. The null and alternative statistical hypotheses for the primary safety endpoint will be defined as follows:

$H_0: Ps \leq PG_S$  versus  $H_A: Ps > PG_S$ ,

where  $Ps$  is the population primary safety success rate in the Test group and  $PG_S$  is the safety performance goal.

The study will be considered a success if the primary effectiveness and primary safety endpoints meets their respective performance goals, translating into the observation of a one-sided 97.5% lower confidence limits of the point estimate above 72% and 82%, respectively.

